#### 4.5. Blinding

This study is an open-label study so blinding is not applicable; however, performing aggregate summaries of efficacy data by treatment arm will be restricted until database lock.

#### 4.6. Study Steering Committee

A Study Steering Committee, composed of experts in the field of hemophilia, will advise the Sponsor on study design and conduct. In collaboration with the Sponsor, the committee will provide scientific leadership to the study to ensure that the highest standards are maintained.

Clinical Advisors who are experts in the care of hemophilia patients and familiar with fitusiran will be available to discuss clinical aspects of care with Investigators for surgical cases, cases of thrombosis, or other medically complex circumstances that may arise on study, when clinical circumstances allow. Such discussions will also look to involve the study Medical Monitor.

#### 4.7. Data Monitoring Committee

An independent DMC will oversee the safety and overall conduct of this study, providing input to the Sponsor. The DMC will operate under the rules of a charter that will be reviewed and approved at the organizational meeting of the DMC. The DMC has the responsibility for reviewing safety data and analyses and making recommendations to the Sponsor. The DMC will perform periodic reviews of data during the course of the clinical trial, and on an ad hoc basis for review of emergent safety data, as defined in the DMC Charter for this clinical trial.

### 5. SELECTION AND WITHDRAWAL OF PATIENTS

#### 5.1. Inclusion Criteria

Each patient must meet all of the following inclusion criteria to be eligible for enrollment in the study:

1. Males  $\geq 12$  years of age.
2. Severe hemophilia A or B with inhibitors evidenced by:
  - a. A central laboratory measurement or documented medical record evidence of FVIII  $< 1\%$  or FIX level  $\leq 2\%$  at Screening.
  - b. On-demand use of BPAs to manage bleeding episodes for at least the last 6 months prior to Screening, and meet one of the following Nijmegen-modified Bethesda assay results criteria:
    - Inhibitor titer of  $\geq 0.6$  BU/mL at Screening, or
    - Inhibitor titer of  $< 0.6$  BU/mL at Screening with medical record evidence of 2 consecutive titers  $\geq 0.6$  BU/mL, or
    - Inhibitor titer of  $< 0.6$  BU/mL at Screening with medical record evidence of anamnestic response
3. A minimum of 6 bleeding episodes requiring BPA treatment within the last 6 months prior to Screening.

- 
4. Willing and able to comply with the study requirements and to provide written informed consent and assent in the case of patients under the age of legal consent, per local and national requirements.

## 5.2. Exclusion Criteria

Each patient must not meet any of the following exclusion criteria to be eligible for enrollment in the study:

1. Known co-existing bleeding disorders other than hemophilia A or B, ie, Von Willebrand's disease, additional factor deficiencies, or platelet disorders.
2. Current participation in immune tolerance induction therapy (ITI)
3. Current use of BPAs as regularly administered prophylaxis designed to prevent spontaneous bleeding episodes.
4. AT activity <60% at Screening, as determined by central laboratory measurement.
5. Presence of clinically significant liver disease, or as indicated by any of the conditions below:
  - a. INR >1.2
  - b. ALT and/or AST >1.5× upper limit of normal reference range (ULN);
  - c. Total bilirubin >ULN (>1.5× ULN in patients with Gilbert's Syndrome);
  - d. History of portal hypertension, esophageal varices, or hepatic encephalopathy;
  - e. Presence of ascites by physical exam
6. Hepatitis C virus antibody positive, except patients with a history of HCV infection who meet both conditions a. and b.:
  - a. Completed curative treatment at least 12 weeks prior to enrollment and attained sustained virologic response as documented by a negative HCV RNA at screening, or they have spontaneously cleared infection as documented by negative HCV RNA at Screening.
  - b. No evidence of cirrhosis according to one of the following assessments:
    - FibroScan <12.5 kPa (where available), or
    - FibroTest score <0.75 and APRI <2 (if FibroScan unavailable)
7. Presence of acute hepatitis, ie, hepatitis A, hepatitis E.
8. Presence of acute or chronic hepatitis B infection (IgM anti-HBc antibody positive or HBs Ag positive).
9. Platelet count ≤100,000/μL.
10. Presence of acute infection at Screening.
11. Known to be HIV positive with CD4 count <200 cells/μL.
12. Estimated glomerular filtration rate ≤45 mL/min/1.73 m^2 (using the Modification of Diet in Renal Disease [MDRD] formula).

- 
13. Co-existing thrombophilic disorder, as determined by presence of any of the below as identified at central laboratory (or via historical results, where available):
    - a. FV Leiden mutation (homozygous or heterozygous)
    - b. Protein S deficiency
    - c. Protein C deficiency
    - d. Prothrombin mutation (G20210A; homozygous or heterozygous)
  14. History of antiphospholipid antibody syndrome.
  15. History of arterial or venous thromboembolism, atrial fibrillation, significant valvular disease, myocardial infarction, angina, transient ischemic attack, or stroke. Patients who have experienced thrombosis associated with indwelling venous access may be enrolled.
  16. Had a malignancy within 2 years, except for basal or squamous cell carcinoma of the skin that has been successfully treated.
  17. Any condition (eg, medical concern), which in the opinion of the Investigator, would make the patient unsuitable for dosing on Day 1 or which could interfere with the study compliance, the patient's safety and/or the patient's participation in the completion of the treatment period of the study. This includes significant active and poorly controlled (unstable) cardiovascular, neurologic, gastrointestinal, endocrine, renal or psychiatric disorders unrelated to hemophilia identified by key laboratory abnormalities or medical history.
  18. At Screening, anticipated need of surgery during the study or planned surgery scheduled to occur during the study.
  19. Completion of a surgical procedure within 14 days prior to Screening, or currently receiving additional BPA infusion for postoperative hemostasis.
  20. History of multiple drug allergies or history of allergic reaction to an oligonucleotide or GalNAc.
  21. Inadequate venous access, as determined by the Investigator, to allow the blood draws required by the study protocol.
  22. History of intolerance to SC injection(s).
  23. Current or future participation in another clinical study, scheduled to occur during this study, involving an investigational product other than fitusiran or an investigational device; in order to participate in this study, patient must discontinue the investigational product or investigational device at least 30 days (or 5× the investigational product half-life, whichever is longer) prior to dosing (Day 1).
  24. Current or prior participation in a gene therapy trial.
  25. History of alcohol abuse within the 12 months before Screening. Alcohol abuse is defined as regular weekly intake of more than 14 units (unit: 1 glass of wine [approximately 125 mL] = 1 measure of spirits (approximately 1 fluid ounce) = ½ pint of beer [approximately 284 mL]).

### 5.3. Removal from Therapy or Assessment

Patients or their legal guardian (in case patient is a minor) are free to discontinue treatment or withdraw from the study at any time and for any reason, without penalty to their continuing medical care. Any discontinuation of treatment or withdrawal from the study must be fully documented in the electronic case report form (eCRF), and should be followed up by the Investigator. The Investigator may withdraw a patient at any time if this is considered to be in the patient's best interest.

Procedures for discontinuation of IMP and/or withdrawal from the study are described in Section 5.3.1 and Section 5.3.2, respectively.

#### 5.3.1. Discontinuation of Investigational Medicinal Product

The Investigator or designee may discontinue dosing in a patient if the patient:

- Is in significant violation of the protocol
- Is non-adherent to treatment regimen
- Experiences a serious or intolerable AE including a life-threatening bleeding episode, eg, any gastrointestinal hemorrhage or intracranial hemorrhage, or life-threatening thromboembolic event
- Requires a prohibited medication.

The Investigator will confer with the Sponsor or study Medical Monitor before discontinuing dosing in the patient.

Patients (or their guardians) may decide to discontinue IMP.

In general, patients who discontinue IMP dosing for any reason will be encouraged to remain on the study to complete the remaining assessments through the end of study so that their experiences are captured in the final analyses. If a patient discontinues dosing due to a serious adverse event (SAE), the SAE should be followed as described in Section 7.5.6. When a patient discontinues IMP dosing, the primary reason must be recorded in the appropriate section of the eCRF. Patients who discontinue IMP but who remain on study may receive treatment consistent with local standard practice for their disease per Investigator judgement, as applicable. Safety will be captured for the entire duration of study for patients who discontinue treatment.

#### 5.3.2. Withdrawal From Study

A patient or guardian may withdraw consent from study participation at any time. The Investigator may withdraw a patient at any time if this is considered to be in the patient's best interest. Any withdrawal from the study must be fully documented in the eCRF, and should be followed-up by the Investigator.

However, study integrity and interpretation is best maintained if all enrolled patients continue study assessments and follow-up even if study treatment is discontinued. Patients considering withdrawing from the study should be informed that they can discontinue treatment and still remain in the study to complete study assessments and follow-up as specified in the Schedule of Assessments (Table 1). If a patient still chooses to discontinue study treatment and withdraw from all follow-up, every effort should be made to conduct the EOS/ET assessments within 4

---

weeks of the last dose (see [Table 1](#)). When a patient withdraws from the study, the withdrawal of consent and the reason for withdrawal must be recorded in the appropriate section of the eCRF and all efforts will be made to complete and report the observations as thoroughly as possible. There will be no replacements of patients who withdraw from this study.

## **6. TREATMENTS**

### **6.1. Treatments Administered**

Investigational medicinal product supplied for this study must not be used for any purpose other than the present study and must not be administered to any person not enrolled in the study. Investigational medicinal product that has been dispensed to a patient and returned unused must not be re-dispensed to a different patient.

### **6.2. Investigational Medicinal Product**

Detailed information describing the preparation, administration, and storage of fitusiran is provided in the Pharmacy Manual.

#### **6.2.1. Description**

Fitusiran (SAR439774) solution for injection (SC use) will be supplied as a sterile solution (see Pharmacy Manual for further details of solution concentration and fill volume).

#### **6.2.2. Dose and Administration**

Patients randomized to the fitusiran treatment arm receive open-label 80 mg fitusiran as an SC injection once monthly, for a total of 9 months; dosing will begin on Day 1 of the treatment period.

Investigational medicinal product injection will be administered at the clinic by qualified staff under the supervision of the Investigator or designee. Detailed instructions for IMP administration are found in the Pharmacy Manual.

Investigational medicinal product will not be blinded as this is an open-label study. See [Section 6.2.5](#) regarding packaging and labeling.

If a patient does not receive a fitusiran dose within the specified dosing window ([Table 1](#)), the Investigator should contact the study Medical Monitor. After such consultation, the dose may be administered or considered missed and not administered.

If a patient misses a dose, the Investigator, in consultation with the study Medical Monitor, will discuss whether the patient will be able to continue on the study.

Additional details regarding dosing can be found in the Pharmacy Manual.

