>5× to 8× ULN	
 
• Hold fitusiran dose until recovery to ≤1.5× ULN; may resume dosing after discussion with the Medical Monitor
 
• Evaluate the initial elevation in LFT per the following assessments: 
 
• Table 6 (all assessments to be performed once)
 
• Hematology, serum chemistry, LFT, and coagulation per Table 5
 
• AT
 
 
 
• Monitor at least weekly (hematology, serum chemistry, LFT, and coagulation per Table 5 and AT) until ALT and/or AST is declining on two consecutive draws, then may decrease monitoring to biweekly
 
• If ALT or AST rises to >5× ULN following repeat dosing, permanently discontinue dosing
 

>8× ULN	Permanently discontinue dosing after confirmation of the transaminase value

Note: In addition to these criteria, other assessments or evaluations may be performed per Investigator discretion, as appropriate.

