### *Fitusiran Treatment During the Perioperative Evaluation Period*

For reference, see Appendix (Section 11.2.1) for definitions of minor and major surgery.

If the need for a major surgery arises during the trial and the procedure is not an emergency or urgent, it is recommended that the procedure be postponed until after completion of the trial.

For minor operative procedures, dosing with fitusiran may continue uninterrupted.

If the need for emergency or urgent major surgery arises during the trial, the patient should be managed medically according to the guidelines above. If a fitusiran dose is scheduled to occur on or in close proximity to the day of surgery, or anytime during the perioperative period, the dose should be withheld. The Perioperative Evaluation Period is defined as the day of the surgery through the final day on which supplemental hemostatic or antithrombotic treatments are administered as part of the perioperative treatment plan. Fitusiran dosing may be resumed at the next scheduled visit following the Perioperative Evaluation Period at the discretion of the Investigator. If multiple consecutive doses of fitusiran are withheld, the Investigator will consult with the study Medical Monitor, who will determine if the patient may continue on study.

Perioperative assessments will be performed in patients undergoing surgery during the study as described in Appendix Section 11.2.2 and as scheduled in Table 10.

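### The missed-dose and perioperative withheld-dose rules tie study participation to dosing, in the fitusiran arm only, and need reconciling with the protocol's policy of follow-up after dosing stops

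*Protocol*

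**What the plan says.** Two clauses link a dosing problem to study participation. Under Protocol Section 6.2.2, a dose not given in its window may be classed as missed after consultation; the Investigator, with the study Medical Monitor, then "will discuss whether the patient will be able to continue on the study". Under Section 6.6 (fitusiran treatment in the perioperative period), if multiple consecutive doses are withheld around emergency or urgent major surgery, "the Investigator will consult with the study Medical Monitor, who will determine if the patient may continue on study".

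Other parts of the protocol keep the two matters apart. Section 5.3.1 covers stopping the product and Section 5.3.2 covers leaving the study. Section 5.3.1 says that, in general, "patients who discontinue IMP dosing for any reason will be encouraged to remain on the study to complete the remaining assessments". Section 5.3.2 gives the reason: "study integrity and interpretation is best maintained if all enrolled patients continue study assessments and follow-up even if study treatment is discontinued". Table 1 footnote b likewise provides for fitusiran patients who stop dosing but agree to complete the remaining assessments and antithrombin (AT) follow-up.

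The analyses rely on that follow-up to different degrees:
- The protocol's primary analysis (Section 8.2.5.1) counts bleeds recorded after fitusiran is discontinued.
- The SAP's treatment-policy analysis (Section 6.3.1.2) uses bleeds to the end of the study whatever happened to dosing.
- The SAP's primary, on-treatment analysis (Sections 6.3 and 6.3.1.1) drops time beyond 28 days after treatment discontinuation. It does not list a missed or temporarily withheld dose as an intercurrent event.

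**The concern.** A decision about whether to go on dosing and a decision about whether to go on observing are different decisions, and the protocol says so in Section 5.3. Sections 6.2.2 and 6.6 use the language of the second for an event that belongs to the first. If the clauses are meant as written, they sit badly with Section 5.3. If they were meant to refer to dosing, they are misworded. Either way the text needs attention.

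The statistical stake is missing bleed data in one arm. On-demand patients have no fitusiran doses to miss, so the dosing trigger cannot apply to them. Those exposed to it are fitusiran patients with a missed visit, a complication or urgent surgery. Their later bleeding may differ from that of the rest of the arm, and treatment is open-label when the decision is taken.

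**Working it through.** **The plan's own figure, as background.** Inputs from Protocol Section 8.1: ABR 18 (SD 14) with 14 evaluable on-demand patients, ABR 4 (SD 6) with 28 evaluable fitusiran patients, two-sided alpha 0.05. A Wald test on the log rate ratio has SE = √[(14/18)²/14 + (6/4)²/28] = 0.352 and effect ln(18/4) = 1.504. Power is 99.0%, which agrees with the stated figure of more than 90%. With 24, 20 or 15 fitusiran patients it is 98.2%, 96.8% or 92.8%. Power is therefore not what is at stake; the question is bias.

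**Days lost.** The efficacy period is Day 29 to Day 246: 246 − 29 + 1 = 218 days. Dosing days come from Table 1.
- Removal after a missed dose on Day 57: 246 − 57 = 189 days; 189/218 = 87%.
- Removal after doses withheld on Days 113 and 141: 246 − 141 = 105 days; 105/218 = 48%.

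Each such patient is 1 of 36 in the fitusiran arm (2.8%).

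**Which analysis loses them.**
- *SAP treatment-policy analysis:* all 189 or 105 days, since it excludes only events due to surgery.
- *Protocol primary analysis:* the same days when the trigger is a missed dose. When the trigger is urgent major surgery, Section 8.2.5.1 already excludes data during and after the surgery. Read literally, those 105 days would be out of that analysis anyway.
- *SAP on-treatment primary, dosing would have resumed:* the days would have counted (less any perioperative period) and are lost.
- *SAP on-treatment primary, dosing stopped for good:* only the 28-day tail is at risk. If discontinuation is dated Day 57, Days 58–85 are lost; if dated Day 141, Days 142–169. Each is 28/218 = 13%. If it is dated from the last dose given (Day 29 or Day 85), the tail ends on Day 57 or Day 113 and nothing is lost. The range is 0 to 28 days.

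**Possible bias (assumptions, not figures from the documents).** Let a share f of the fitusiran arm be removed halfway through the efficacy period, with a true later ABR of r. The full-follow-up fitusiran ABR is (1 − f/2) × 4 + (f/2) × r; dividing by 18 gives the rate ratio.

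| f | r = 4 | r = 8 | r = 18 |
|---|---|---|---|
| 5% | 0.222 | 0.228 | 0.242 |
| 10% | 0.222 | 0.233 | 0.261 |
| 20% | 0.222 | 0.244 | 0.300 |

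Treating the lost time as missing at random would give about 4/18 = 0.222 in every row. For f = 10% and r = 8: 0.95 × 4 + 0.05 × 8 = 4.2, and 4.2/18 = 0.233. There is no bias if later bleeding stays at the arm's average.

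**The case against.** The strongest reply is that nothing in the text requires removal. Section 6.2.2 asks for a discussion. Section 6.6 needs multiple consecutive withheld doses. Section 5.3 itself encourages follow-up rather than mandating it. Withdrawal by the Investigator is already possible in either arm: "The Investigator may withdraw a patient at any time if this is considered to be in the patient's best interest". The SAP's Covid-19 sensitivity analysis (Section 6.3.1.2) provides for patients who miss at least two consecutive doses and are later re-dosed, so missed doses are not treated as automatic exit. The same section plans multiple imputation for the treatment-policy analysis, under missing at random and under copy reference. All of this stands and limits the point. It does not remove the mismatch: only the two dosing clauses make a missed or withheld dose the occasion for deciding on study participation. Imputation also replaces bleeds that could have been recorded.

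Four stronger readings are tempting, and the documents do not support them.
- *A required liver hold leads to removal.* Table 3 says "Hold fitusiran dose until recovery to ≤1.5× ULN" and has its own route to resumption. The protocol speaks separately of doses held, withheld and missed. Getting from a Table 3 hold to the missed-dose clause is an interpretation.
- *The sponsor decides who stays.* The text says study Medical Monitor, and Section 5.3.1 names the Sponsor and the Medical Monitor as alternatives.
- *Safety follow-up is cut off.* Serious events are followed to resolution or stability (Sections 7.5.6.2 and 7.5.6.3), and Section 5.3.2 asks for every effort to complete the final visit. What is exposed is scheduled laboratory, AT and non-serious adverse event follow-up.
- *The SAP primary analysis loses 48% or 87% of a patient's data.* That holds only if the patient would have resumed dosing.

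**Conclusion.** The inconsistency is real and worth correcting. Sections 6.2.2 and 6.6 tie a fitusiran dosing problem to study participation, while Section 5.3 and Table 1 footnote b separate the two. The trigger can operate in one arm only, so its use could produce avoidable, event-related missing bleed data there.

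The per-patient loss is large in the treatment-policy analysis and, for a missed dose, in the protocol's primary analysis. In the SAP's on-treatment primary analysis it is small or nil unless dosing would have resumed. How many patients would be affected cannot be known from the documents. Under the illustrative assumptions the rate ratio moves from 0.222 to no more than 0.300, so the documents do not support a claim that the trial's conclusion would change. The case for acting is that the correction costs little and protects data that two of the planned analyses depend on.

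**What to change.** Reconcile Sections 6.2.2 and 6.6 with Sections 5.3.1 and 5.3.2, so that study follow-up is stated separately from any decision about dosing. State that a missed or withheld dose is not in itself a reason to end eDiary, adverse event and AT follow-up.

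Leave the patient's right to withdraw consent and the Investigator's best-interest withdrawal (Sections 5.3 and 5.3.2) as they are. No dosing, holding or stopping rule is proposed or changed, nor is who decides on dosing.

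The cost is a clarification in two places at the next amendment. It adds no visits to those already in Table 1.

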#### **6.2.3. Dose Modifications**

No fitusiran dose modifications will be allowed.

---

If a IMP-related AE occurs in a patient that the Investigator judges as presenting a potential risk to the patient for further dosing, the fitusiran dose may be held at the discretion of the Investigator and the study Medical Monitor should be contacted.

#### 6.2.3.1. LFT Criteria for Withholding, Monitoring and Stopping Fitusiran Dosing

1. LFT results are to be obtained within 7 days prior to dosing and results are to be reviewed prior to each dose of fitusiran. Central laboratory results are preferable. If not available, local laboratory results may be used; however, if a local assessment is drawn, a serum chemistry sample must also be drawn for analysis at the central laboratory.
2. For any ALT or AST elevation  $>3 \times$  ULN, central laboratory results should be used to guide subsequent monitoring as detailed in [Table 3](#).
3. For any ALT or AST elevation  $>3 \times$  ULN:
  - a. Confirm using central laboratory, as soon as possible, ideally within 2 to 3 days, but no later than 7 days.
  - b. Perform assessments per [Table 3](#) and [Table 6](#).
  - c. If an alternative cause is found, provide appropriate care.
4. For any ALT or AST elevation  $>3 \times$  ULN without alternative cause that is accompanied by clinical symptoms consistent with liver injury (eg nausea, right upper quadrant abdominal pain, jaundice) or elevated bilirubin to  $\geq 2 \times$  ULN or INR  $\geq 1.5$ , permanently discontinue dosing.
5. For confirmed ALT or AST elevations  $>3 \times$  ULN without alternative cause and not accompanied by symptoms or elevated bilirubin  $\geq 2 \times$  ULN or INR  $\geq 1.5$ , see [Table 3](#) below:

**Table 3: Monitoring and Dosing Rules for Asymptomatic Patients with Confirmed Isolated Elevations of ALT and/or AST >3× ULN, with No Alternative Cause Identified**

Transaminase Level	Action
>3× to 5× ULN	
 
• May continue dosing
 
• Evaluate the initial elevation in LFT per the following assessments: 
 
• Table 6 (all assessments to be performed once)
 
• Hematology, serum chemistry, LFT, and coagulation per Table 5
 
• AT
 
 
 
• Monitor at least every two weeks (hematology, serum chemistry, LFT, and coagulation per Table 5 and AT)
 
• If elevation persists for ≥2 months, must discuss with the study Medical Monitor before continuing dosing
 

>5× to 8× ULN	
 
• Hold fitusiran dose until recovery to ≤1.5× ULN; may resume dosing after discussion with the Medical Monitor
 
• Evaluate the initial elevation in LFT per the following assessments: 
 
• Table 6 (all assessments to be performed once)
 
• Hematology, serum chemistry, LFT, and coagulation per Table 5
 
• AT
 
 
 
• Monitor at least weekly (hematology, serum chemistry, LFT, and coagulation per Table 5 and AT) until ALT and/or AST is declining on two consecutive draws, then may decrease monitoring to biweekly
 
• If ALT or AST rises to >5× ULN following repeat dosing, permanently discontinue dosing
 

>8× ULN	Permanently discontinue dosing after confirmation of the transaminase value

Note: In addition to these criteria, other assessments or evaluations may be performed per Investigator discretion, as appropriate.

